14.1.16 Efficacy definitions

The following definitions primarily relate to patients who have measurable disease at baseline. [Section 14.1.26](#) outlines the special considerations that need to be given to patients with no measurable disease at baseline in order to apply the same concepts.

14.1.17 Best overall response

The best overall response is the best response recorded from the start of the treatment until disease progression/recurrence (taking as reference for PD the smallest measurements recorded since the treatment started). In general, the patient's best response assignment will depend on the achievement of both measurement and confirmation criteria.

The best overall response will usually be determined from response assessments undertaken while on treatment. However, if any assessments occur after treatment withdrawal the protocol should specifically describe if these will be included in the determination of best overall response and/or whether these additional assessments will be required for sensitivity or supportive analyses. As a default, any assessments taken more than 28 days after the last dose of study therapy will not be included in the best overall response derivation. If any alternative cancer therapy is taken while on study any subsequent assessments would ordinarily be excluded from the best overall response determination. If response assessments taken after withdrawal from study treatment and/or alternative therapy are to be included in the main endpoint determination then this should be described and justified in the protocol.

Where a study requires a response PR or CR, changes in tumor measurements must be confirmed by repeat assessments that should be performed not less than 4 weeks after the criteria for response are first met.

Longer intervals may also be appropriate. However, this must be clearly stated in the protocol. The main goal of confirmation of objective response is to avoid overestimating the response rate observed. In cases where confirmation of response is not feasible, it should be made clear when reporting the outcome of such studies that the responses are not confirmed.

- For non-randomized trials where response is the primary endpoint, confirmation is needed.
- For trials intended to support accelerated approval, confirmation is needed.
- For all other trials, confirmation of response may be considered optional.

The best overall response for each patient is determined from the sequence of overall (lesion) responses according to the following rules:

- CR = at least two determinations of CR at least 4 weeks apart before progression where confirmation required or one determination of CR prior to progression where confirmation not required
- PR = at least two determinations of PR or better at least 4 weeks apart before progression (and not qualifying for a CR) where confirmation required or one determination of PR prior to progression where confirmation not required

- SD = at least one SD assessment (or better) > 6 weeks after randomization/start of treatment (and not qualifying for CR or PR).

The protocol should state if randomization or start of treatment is used as start date (baseline). This is then used in all definitions.

If a different minimum follow-up period is required to classify for overall response= 'stable disease', this must be specified in the protocol.

- PD = progression ≤ 12 weeks after randomization/ start of treatment (and not qualifying for CR, PR or SD).

If PD in a different follow-up period is considered overall response='progressive disease', this must be specified in the protocol.

The protocol should state if discontinuation due to 'Disease progression' or death due to study indication is considered PD even if this was not accompanied by documentation of PD based on tumor measurements. This depends on Phase of the study and the primary endpoint (e.g. Phase III studies in which progression-free survival is primary endpoint should consider only documented PD, whereas Phase I and II studies may consider all clinical deteriorations PD). The following sentence therefore is only applicable if this is specified in the protocol:

- Patients with symptoms of rapidly progressing disease without radiologic evidence will be classified as progression only when clear evidence of clinical deterioration is documented and/or patient discontinued due to 'Disease progression' or death due to study indication.
- UNK = all other cases (i.e. not qualifying for confirmed CR or PR and without SD after more than 6 weeks or early progression within the first 12 weeks)

Overall lesion responses of CR must stay the same until progression sets in, with the exception of a UNK status. A patient who had a CR cannot subsequently have a lower status other than a PD, e.g. PR or SD, as this would imply a progression based on one or more lesions reappearing, in which case the status would become a PD.

Once an overall lesion response of PR is observed (which may have to be a confirmed PR depending on the study) this assignment must stay the same or improve over time until progression sets in, with the exception of an UNK status. However, in studies where confirmation of response is required, if a patient has a single PR (≥30% reduction of tumor burden compared to baseline) at one assessment, followed by a <30% reduction from baseline at the next assessment (but not ≥20% increase from previous smallest sum), the objective status at that assessment should be SD. Once a confirmed PR was seen, the overall lesion response should be considered PR (or UNK) until progression is documented or the lesions totally disappear in which case a CR assignment is applicable. In studies where confirmation of response is not required after a single PR the overall lesion response should still be considered PR (or UNK) until progression is documented or the lesion totally disappears in which case a CR assignment is applicable.

Example: In a case where confirmation of response is required the sum of lesion diameters is 20 cm at baseline and then 14 cm - 15 cm - 14 cm - 16 cm - 16 cm at the subsequent visits. Assuming that non-target lesions did not progress, the overall lesion response would be PR - SD - PR - PR - PR. The second assessment with 14 cm confirms the PR for this patient. All

subsequent assessments are considered PR even if tumor measurements decrease only by 20% compared to baseline (20 cm to 16 cm) at the following assessments.

If the patient progressed but continues study medication, further assessments are not considered for the determination of best overall response.

Note: these cases may be described as a separate finding in the Clinical Study Report but not included in the best overall response rate.

The best overall response for a patient is always calculated, based on the sequence of overall lesion responses. However, the overall lesion response at a given assessment may be provided from different sources:

- Investigator overall lesion response
- Central Blinded Review overall lesion response
- Calculated overall lesion response (based on measurements from either Investigator or Central Review)

The primary analysis of the best overall response will be based on the sequence of Investigator/central blinded review/calculated (Investigator)/calculated (central) overall lesion responses.

Specify which determination of best overall response will be considered primary (and delete the other terms in the text). If a central blinded review is used (e.g. in an open-label study in which response is the primary endpoint), the best overall response evaluated by the central blinded review will always be considered the primary response.

Based on the patients' best overall response during the study, the following rates are then calculated:

Overall response rate (ORR) is the proportion of patients with a best overall response of CR or PR. This is also referred to as 'Objective response rate' in some protocols or publications.

Disease control rate (DCR) is the proportion of patients with a best overall response of CR or PR or SD.

Another approach is to summarize the progression rate at a certain time point after baseline. In this case, the following definition is used:

Early progression rate (EPR) is the proportion of patients with progressive disease within 8 weeks of the start of treatment.

The protocol should define populations for which these will be calculated. The timepoint for EPR is study specific. EPR is used for the multinomial designs of (Dent and Zee 2001) and counts all patients who at the specified assessment (in this example the assessment would be at 8 weeks \pm window) do not have an overall lesion response of SD, PR or CR. Patients with an unknown (UNK) assessment at that time point and no PD before, will not be counted as early progressors in the analysis but may be included in the denominator of the EPR rate, depending on the analysis population used. Similarly when examining overall response and disease control, patients with a best overall response assessment of unknown (UNK) will not be regarded as "responders" but may be included in the denominator for ORR and DCR calculation depending on the analysis population (e.g. populations based on an ITT approach).

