7.2 Assessment types

7.2.1 Efficacy assessments

Tumor response will be evaluated locally by the investigator according to the guideline based on RECIST version 1.1 (see [Appendix 1](#)). Each subject will be evaluated for all potential sites of tumor lesions at Screening/baseline, at the end of Cycle 1 (not applicable for patients enrolled

in the Phase II part of the study) and Cycle 2 and then every 8 weeks (2 cycles) thereafter during the study treatment until disease progression. Screening/baseline imaging assessments may be performed within 21 days of treatment start, except whole-body bone scans, if applicable, which can be performed within 6 weeks of treatment start. On-study tumor assessments have a ± 7 day window, except for the tumor assessment on C1D28 which must be performed between week 3 and 4 after starting the study drug combination. Patients who have been on the LGX818/MEK162 dual- or triple-combination treatment for ≥ 24 months (Cycle 25 Day 1 onward) will be evaluated for all potential sites of tumor lesions every 8-12 weeks (± 7 days) until disease progression.

There will be a tumor assessment at End of Treatment (± 3 days) if the patient discontinues for any reason other than disease progression and the last tumor assessment has been performed > 21 days prior to this day. Subjects included in the Phase II part of the study, who discontinue study treatment due to another reason than disease progression, should be followed up monthly via a phone call and undergo tumor assessments every 8 weeks (± 7 days) until disease progression or initiation of subsequent anti-neoplastic therapy, or death, whichever occurs first ([Section 7.1.5.2](#)). Patients who have been on either dual- or triple-combination treatment for ≥ 24 months (Cycle 25 Day 1 onward) and then discontinue study treatment for any reason other than disease progression will have CT/MRI scans every 8-12 weeks (± 7 days).

At Screening/baseline the following should be performed:

- A CT scan with intravenous (i.v.) contrast of chest, abdomen and pelvis is required for all patients.
- In subjects with a history of asymptomatic brain metastases, a brain MRI or CT scan must be performed.

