- In subjects participating in the triple-combination part of the study a brain MRI or CT with intravenous (i.v.) contrast scan to assess CNS disease must be performed. Contrast enhanced brain MRI is preferred, however, if MRI contrast is contraindicated, then brain MRI without contrast or brain CT with/without contrast is acceptable.
- If clinically indicated, a whole-body bone scan (i.e., if bone metastases are suspected or known at baseline) should be performed. Sites may use a whole-body bone imaging method per their local standard-of-care (e.g., Tc99m bone scan, NaF PET scan, or whole-body bone MRI). Skeletal lesions identified on a whole-body bone scan at baseline, which are not visible on the chest, abdomen and pelvis CT (or MRI) scan should be imaged at baseline using localized CT, MRI or x-ray.
- Color photography if skin lesions are present (it is recommended to include a ruler to estimate the size of the lesion).

Every effort must be made to assess each lesion that is measured at Screening/baseline by the same method throughout the study so that the comparison is consistent.

At all post-Screening/baseline assessments the following should be performed:

- All patients are required to undergo chest, abdomen and pelvis CT or MRI scans.
- Brain MRI or CT scan, if metastases were documented at baseline.
- Skeletal lesions identified at baseline should continue to be imaged at subsequent scheduled visits using localized CT, MRI or x-ray if not visible on the chest, abdomen and

pelvis CT or MRI scan. After baseline, whole-body bone scans need not be repeated, unless clinically indicated.

- Color photography of any skin lesions documented at baseline (it is recommended to include a ruler to estimate the size of the lesion).
- Additional tumor assessments (e.g. MRI or CT of the brain) may be performed if there is symptomatic evidence suggesting the possibility of disease progression based on clinical symptoms or physical exam at any time.

Criteria required for determining partial or complete response should be present for at least 4 weeks. All complete and partial responses must be confirmed by a second assessment at least 4 weeks later. Note: sites must make sure for patients enrolled in the Phase Ib part of the study that at least 4 weeks are scheduled between the tumor assessments on C1D28 and C2D28 to allow confirmation of response.

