10.4.2.2 Phase II

Efficacy will be assessed using the local CT/MRI assessments evaluated under RECIST version 1.1, [Appendix 1](#). The Best Overall Response (BOR) for each patient and individual lesion measurements will be listed. The (BOR) is the best response recorded from the start of the treatment until disease progression. Based on patients' BOR during study, the Objective Response Rate (ORR) and the Disease control Rate (DCR) are then calculated.

The ORR is defined as the proportion of patients with a best overall response of Complete Response (CR) or Partial Response (PR). The DCR is defined as CR or PR or Stable Disease (SD).

Patients who withdrew prematurely due to progression of disease without having any post-dose tumor assessment will be classified as treatment failures. Similarly, patients who died due to their disease without having any post-dose tumor assessment will be classified as treatment failures.

Arm 1 dual combination: patients with metastatic BRAF V600 mutant mCRC

A Bayesian design will be used in order to estimate the true DCR. Inferential statements will be based on the uncertainty of this quantity. For a Bayesian design it is required to specify a prior distribution for the parameter of interest, in this case DCR.

For the current study, the prior clinical assumption for a MEK inhibitor in BRAF V600 mutant mCRC at pre-specified dose-levels will be used in order to derive a minimally informative unimodal Beta prior distribution that reflects the level of uncertainty around the DCR before starting the current trial. At completion of the study, this prior distribution will be updated with all the data available in this part of the study.

Once updated, the distribution summarizes the probability that the true DCR at the dose of the LGX818 and MEK162 combination used in the Phase II lies in the following categories:

- [0, 20%) unacceptable efficacy
- [20%, 30%) limited efficacy
- [30%, 40%) moderate efficacy
- [40%, 100%] clinically relevant efficacy

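### Under the 28-day default in Appendix 1, a response first seen shortly before treatment stops cannot be confirmed in time to count in the primary ORR of arms 2, 3 and A

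*Protocol*

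**What the plan says.** Section 10.4.2.2 gives the definition behind the primary ORR: "The (BOR) is the best response recorded from the start of the treatment until disease progression". It evaluates response under Appendix 1 and does not mention scans after the last dose.

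Appendix 1, section 14.1.17, opens with the same definition and then turns to assessments made after treatment withdrawal. On these, "the protocol should specifically describe if these will be included in the determination of best overall response". The fallback rule reads: "any assessments taken more than 28 days after the last dose of study therapy will not be included in the best overall response derivation". Assessments after alternative cancer therapy are ordinarily excluded as well.

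Section 7.2.1 sets the Phase II scans. There is none at the end of Cycle 1. The first is at the end of Cycle 2, "then every 8 weeks (2 cycles) thereafter during the study treatment until disease progression". On confirmation: "All complete and partial responses must be confirmed by a second assessment at least 4 weeks later". On stopping: "There will be a tumor assessment at End of Treatment (± 3 days) if the patient discontinues for any reason other than disease progression". This scan is due only when the previous one is more than 21 days old. After such a stop, Phase II patients "undergo tumor assessments every 8 weeks (± 7 days) until disease progression or initiation of subsequent anti-neoplastic therapy". Section 7.1.4 places the End of Treatment (EOT) visit within 14 days of the last dose. If dosing was already interrupted for more than 14 days, the visit follows the decision to discontinue.

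**The concern.** The 28-day limit is shorter than the 8-week scan interval, and equal to the minimum gap between a response and its confirmation. For a patient who stops soon after a first response, the scan that would confirm it can be required by the schedule and still be inadmissible. Such a patient may have a PR on two consecutive scheduled scans, with no progression and no new therapy, and be classed as SD.

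ORR is the primary variable in arms 2, 3 and A, and the success rules are fixed counts: 7 of 41 and 16 of 40. One reclassified patient moves the observed ORR by 1/41 = 2.4 points in arm 2 and 1/40 = 2.5 points in arms 3 and A. Whether the patient counts depends on the visit calendar, not on whether the response was lost.

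**Working it through.** **The plan's own figures.** With X ~ Binomial(n, p), the probability of declaring activity is P(X ≥ r).

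- Arm 2 (n = 41, r = 7): 0.1102 at ORR 10% and 0.7390 at ORR 20%. Section 10.8 states 11.0% and 73.9%.
- Arms 3 and A (n = 40, r = 16): 0.1151 at ORR 30% and 0.9231 at ORR 50%. Section 10.8 states 11.5% and 92.3%.

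All four reproduce.

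**The calendar.** Take a first PR on the end-of-Cycle-2 scan, day 56, and a last dose on day L. A scan on day S confirms and counts only if

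- S ≥ 56 + 28 = 84 (confirmation rule), and
- S ≤ L + 28 (Appendix 1 default).

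Two scheduled scans could qualify.

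- EOT scan: required only if the last scan is more than 21 days old, so from day 78. The visit is at latest on L + 14. Allowing the ±3-day scan window on top, the latest scan is on L + 17.
- Next 8-weekly scan: day 112, with a window of days 105 to 119.

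| Last dose | Can a scheduled scan confirm? |
|---|---|
| Up to day 66 | No. At L = 66 the latest EOT scan is day 83, one day short; the earliest follow-up scan is day 105 against a limit of day 94. |
| Days 67-76 | Only through a late enough EOT scan: at least 84 − L days after the last dose, so 17 days at L = 67 and 8 days at L = 76. The follow-up limit (days 95-104) is still before day 105. |
| Days 77-83 | By an EOT scan 1 to 7 days after the last dose, or by a follow-up scan at the early edge of its window. |
| Day 84 on | Yes. The nominal day-112 scan is within L + 28. |

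The week-8 scan has its own ±7-day window, so the dates are illustrative. Relative to the first response, the loss is certain for stops up to about 10 days later and depends on EOT timing for about days 11 to 20.

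A patient lost in this way is classed as SD, because day 56 is beyond the 6 weeks (42 days) that 14.1.17 requires for SD.

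**Response first seen at EOT.** If the EOT scan is on day E > L, its confirmation can come no earlier than E + 28, which is later than L + 28. Under the default it can never be confirmed.

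**Interruption before the stop.** This can work either way. With a last dose on day 63 and the stop decided and scanned on day 85, the scan is 29 days after the PR and 22 days after the last dose, so it confirms. If the decision comes more than 28 days after the last dose, the EOT scan is itself excluded.

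**Effect on the decision rule.** If a share l of true responders is lost, p becomes p(1 − l). The document gives no value for l; those below are assumed.

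| l | Arm 2, ORR 20% | Arms 3/A, ORR 50% | Arm 2, ORR 10% | Arms 3/A, ORR 30% |
|---|---|---|---|---|
| 0 | 73.9% | 92.3% | 11.0% | 11.5% |
| 2% | 71.8% | 90.3% | 10.2% | 9.9% |
| 5% | 68.5% | 86.6% | 9.0% | 7.8% |
| 10% | 62.5% | 78.6% | 7.1% | 5.1% |

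The last two columns are false-positive probabilities, which also fall.

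**The case against.** A reader might infer that 10.4.2.2 and Appendix 1 contradict each other. They do not. Appendix 1 opens with the same definition, 14.1.1 says it supplies more detailed rules, and 14.1.17 lets off-treatment scans into the main endpoint only if the protocol describes and justifies it. The body is silent, so the default governs. Section 14.1.29 also lets study-specific decisions be fixed in the RAP, which is not at hand and may already settle this.

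A reader might also infer that responders who stop for toxicity become non-responders in general. That is wrong. Confirmed responses stand, and the EOT scan rescues most unconfirmed ones when the stop comes about 3 to 4 weeks or more after the first response. In arm 1 an unconfirmed PR after week 6 still counts as SD, so best-response DCR is not lowered this way.

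On size, the only adverse-event stopping rate to hand is 21% in CMEK162X2201. It covers MEK162 alone, two doses, and responders and non-responders together over the whole of treatment. If it were spread evenly over about 182 days (an assumption), an 11-day window would catch 0.21 × 11/182 = 1.3% and a 21-day window 2.4%. Early clustering of toxicity would raise this, but nothing in the protocol shows it. That points to the lower end of the table, though only loosely.

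The bias is conservative, and limiting response to scans on or shortly after treatment is a legitimate choice. Enrollment has closed and the trial is open-label, so widening the primary derivation now could only raise ORR. These points stand. They bear on size and on how the change is reported. They do not remove the misclassification: the default was adopted without being fitted to this scan schedule.

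**Conclusion.** The point holds for a defined subset. Under the Appendix 1 default, patients in arms 2, 3 and A who stop for a reason other than progression shortly after a first, unconfirmed response are counted as non-responders, even if the next required scan still shows the response. For a first PR on day 56 this is certain on scheduled visits for last doses up to about day 66, and depends on EOT timing for about days 67-76. It also applies to any response first seen on an EOT scan done after the last dose. An interruption of more than 14 days before the stop can move a patient either way.

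The effect lowers ORR. Its size cannot be computed, because the document gives no rate of stopping near first response. Over the assumed 2% to 10% loss, the probability of correctly declaring activity falls by 2.1 to 11.4 points in arm 2 and by 2.0 to 13.7 points in arms 3 and A. A reader might take the upper figures as expected; the documents do not support that. This is an inexpensive improvement to the primary derivation and not a flaw that invalidates the design.

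**What to change.** State in 10.4.2.2, or in the RAP before database lock, which post-treatment scans count for best overall response. The suggested rule is that scans up to progression or the start of new anticancer therapy count, at least to confirm a response first seen on treatment or within 28 days of the last dose. Report ORR both with and without the 28-day restriction, say which was the default, and flag responses confirmed off treatment. Because data are already known, neither version should silently replace the other.

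The cost is a sentence or two and one extra table. The follow-up scans were already required until Amendment 10 ended post-treatment follow-up. The downside is that a few responses will be confirmed off treatment, and a late change to the primary derivation must be disclosed as such.
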